## SAMPLE SIZE

The aim is to recruit 95 participants, including patients (n=30), their carers (n=30), and ward staff (n=35). No power calculation has been undertaken since this feasibility study will evaluate acceptability/feasibility in principle rather than obtaining statistically significant results and will assess progression criteria in a pragmatic but purposively diverse sample of patients/carers/healthcare professionals.

## INCENTIVES AND PAYMENTS

Participants will not receive any payments or incentives for study participation. Individual researchers will not receive any personal payment over and above normal salary, or any other benefits or incentives.

## 8. DESCRIPTION OF THE INTERVENTION

A detailed description of the intervention is provided below, in accordance with TIDieR guidelines (Template for Intervention Description & Replication).

### ***Brief name***

Isla for Frailty

### ***Why: rationale for the intervention***

The lack of secure and efficient ways to acquire, store and share photographs and videos may partly explain why visual data have not been fully exploited in healthcare to date. Yet, visual information

can be very helpful when assessing patients and communicating information about a patient's condition to other healthcare professionals. Video-recordings could support existing verbal and written handovers between care-providers enabling objective and accurate assessments of the frail older person's condition and support needs.

### ***What: materials***

Isla is a technology company providing a visual patient record platform. The platform allows anyone involved in a patient's care to capture and review visual data (photographs, videos) relating to a patient's health. The platform is web-based (a "progressive web application") and supports secure capture of visual data with encrypted storage in the cloud.

To capture visual data using Isla, the user must be logged into the platform on a smartphone/ mobile device with an in-built camera with WiFi connection. Isla's application can be added to the device's homescreen; registered users enter their NHS.net credentials to log in. The device should be connected to the 'eduroam' WiFi network, which is available in the study setting and accessible by all clinical staff with an NHS.net account.

Isla interfaces with Electronic Health Record (EHR) systems including Cerner, enabling health professionals to view data held on Isla's servers from within the electronic patient record, via the 'Cerner Red Button'. Health professionals can also view a patient's visual record through a secure weblink requiring an NHS email address and password.

The Isla visual patient record platform is approved by NHS Digital and satisfies all NHS and ICHT data security and protection requirements (See **Imperial College Healthcare NHS Trust's Data Protection Impact Assessment for Isla**).

### ***What: procedure***

There will be a 3-month pilot of ISLA's visual record platform in the study setting. Isla will be used by the Medicine for the Elderly team to record, store and review video-recordings of patient participants. The videos will capture aspects of the patient's condition/functional ability that the team believes could usefully support care-provider communications and ongoing patient assessment, including:

- Mobility
- Transfers
- Eating and drinking
- Alertness
- Cognitive function (e.g. 4AT assessment or instructional tasks)
- Behaviour
- Communication
- Clinical examinations
- Patient preferences

Note, personal care or toileting will *not* be recorded.

### *Video views by the direct care team*

Patient videos will be available for view by the direct care team during the patient's inpatient stay. The study protocol does not dictate when the videos will be reviewed by members of the direct care team; rather, the study will explore the real-world use of patient videos within the setting. The direct care team will be encouraged to view the videos and to use them in a way that they feel is useful to support patient care – for example, the videos could be used to support communication about a patient's condition/support needs during shift handovers, during ward rounds and MDT meetings, to inform discharge planning, or in discussions with the patients' family members/informal carers.

### *Who*

Videos will be recorded by members of the patient's direct care team (doctors/ nurses/ healthcare assistants/ therapists) in accordance with the **Patient video-recording and Consent Standard**

**Operating Procedure (SOP).** All clinical staff will have received training on Data Security Awareness as part of their statutory and mandatory training in the Trust. Additionally, they will receive training on how to use Isla's visual patient record platform and on the video-recording SOP, at the beginning of the study (see 'Staff engagement & preparation for the pilot' below).

### *How*

#### *Staff engagement & preparation for the pilot*

Extensive staff engagement activities will be undertaken prior to the 3-month pilot of Isla's visual patient record platform in the study setting. The clinical lead for the study and the researcher will present the video-recording initiative to all medical, nursing and allied health professional staff during routine clinical team meetings and during drop-in sessions held by the clinical lead and the researcher on the ward. These engagement activities will take place 2-3 times per week over the course of four weeks to ensure coverage of the full staffing rota. During the staff engagement phase, staff will be provided with information about:

- the aims of the study
- the purpose of the video-recordings
- what staff can expect should they choose to participate in the evaluation of the Isla for Frailty intervention

Further information about staff enrolment procedures and consent are provided in section 7.2.

All permanent clinical staff members who work in the study setting will be registered with Isla prior to the pilot, providing they have consented to this. ICHT healthcare professionals participating in the care transitions review of patient videos will also be registered with Isla.

All healthcare professionals participating in the study will receive training on how to use Isla's platform and how to record patient videos according to the **Video-recording SOP** prior to platform's 'go live' date in the study setting.

The research team will place **study signage** around the ward to indicate to other patients and visitors that eligible patients and staff are participating in a research study involving video-recordings.

## *During the pilot*

Patient enrolment will commence on the go-live date for the Isla platform in the study setting. On completion of enrolment procedures, the researcher will add the patient participants to the patient list in Isla and will flag new study participants to the direct care team at the time of enrolment.

Study participants will be highlighted on the direct care team's handover documentation (iWard or patient jobs list). The following abbreviations will indicate whether or not a patient has video submission available for view from within the electronic patient record in Cerner:

- I4F-0: patient is enrolled in the I4F study, no video submissions
- I4F-V: patient is enrolled in the I4F study, videos available for view

Study participants will be reviewed during daily ward rounds and multidisciplinary team (MDT) meetings; the direct care team will discuss which aspects of the patient's condition/support needs (if any) should be video recorded. The team will agree who among the team has accountability for ensuring the chosen video recording is taken on a case-by-case basis. The decision to record a video will be documented as part of the daily plan in the patient's record on Cerner, on the junior doctors' jobs list, and on the **Video Tracker**.

All patient videos will be recorded in accordance with the video-recording standard operating procedure. Once a video-recording has been taken and submitted to the patient's record, signage will be placed on the wall at the back of the patient's bed (**Signage B**)

## *Where*

Patient videos will be recorded on the Medicine for the Elderly ward or in other areas within St. Mary's hospital where patients' functional abilities are assessed (e.g. hospital staircase, therapy kitchen; therapy gym).

Patient videos will be viewed on an ICHT password-protected computer on Trust premises.

## *When & how much*

There will be no fixed schedule of video-recordings. The frequency of recordings will be at the discretion of the consultant in charge of the direct care team considering the patient's condition. However, as a minimum, video-recordings will be captured when the patient is assessed as 'medically optimised' prior to hospital discharge. The duration of video-recordings will be no longer than five minutes per recording.

There will be no fixed schedule of video viewings by the direct care team. The direct care team will be encouraged to view the videos and to use them in a way that they feel is useful to support patient care – for example, the videos could be used to support communication about a patient's condition/support needs during shift handovers, during ward rounds and MDT meetings, to inform discharge planning, or in discussions with the patients' family members/informal carers.

## *Tailoring*

The content and number of video-recordings will differ between patients due to the heterogeneity of medical conditions, functional abilities, and support needs.

***How well***

Each video-recording request/ attempt/ submission will be documented on the **Video Tracker**. Issues relating to the video-recording process will also be documented on the tracker.

## 9. OUTCOME MEASURES

Primary outcome measure:

- Patient, carer and staff perspectives on the acceptability of video-based records

Secondary outcome measures:

- Recruitment and retention rates
- % of patient participants with videos linked to the electronic patient record
- Video view metrics
- Intervention barriers & facilitators
- Perceived impacts of video-based records on:
  - inpatient assessment & clinical decision-making
  - multi-disciplinary team communication
  - care continuity during a hospital stay
  - person-centred care during a hospital stay
- No. of videos raising cause for concern reported to the clinical lead

**Table 1** (see overleaf) provides a summary of outcomes, measures/ approaches for obtaining data, and analyses (qualitative and quantitative), corresponding to the primary and secondary study objectives. In line with standard feasibility study objectives, clinical outcomes are not examined at this early investigative phase of the project.

Table 1: Summary of outcomes, measures/approaches, and methods of analysis

Objective	Outcomes	Measures/data collection	Methods of analysis
Acceptability	Patient/carer acceptability	
 
- % of eligible participants declining enrolment & reasons for non-participation (screening/enrolment log)
 
- % of enrolled patients with ≥ 1 video linked to the EPR
 
- Semi-structured interview at or within 2 weeks of discharge
 
	Descriptive statistics
	Direct care team acceptability	
 
- Video evaluation questionnaire
 
- Semi-structured interview after the 3-month pilot
 
- No. of videos requested, attempted & submitted (video tracker)
 
	Descriptive statistics Framework analysis Descriptive statistics & Framework analysis Framework analysis
Feasibility	Patient enrolment	
 
-% of eligible participants who were enrolled into the study (screening/enrolment log)
 
- diversity of study sample (screening/enrolment log)
 
	Descriptive statistics
	Intervention barriers & facilitators	
 
- Semi-structured interviews with patients/carers
 
- Semi-structured interviews with direct care team
 
	Framework analysis Framework analysis
	Use of the Isla platform	
 
- % of participants with videos linked to the EPR
 
- Video view metrics
 
	Descriptive statistics Descriptive statistics
	Privacy & security concerns	
 
- No. of videos raising cause for concern reported to the clinical lead
 
	Descriptive statistics Descriptive statistics
Perceived effectiveness	Perceived impacts on: 
 
i) inpatient assessment & clinical decision-making
 
ii) multi-disciplinary team communication
 
iii) care continuity during a hospital stay
 
iv) person-centred care during a hospital stay
 
	
 
- Video evaluation questionnaires
 
- Semi-structured interviews with direct care team after the pilot
 
- Semi-structured interviews with patients/patient-carer dyads at or within 2 weeks of discharge
 
	Descriptive statistics & Framework analysis Framework analysis Framework analysis

EPR = electronic patient record; ICHT = Imperial College Healthcare NHS Trust

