#### **CRITERIA FOR ELECTIVELY STOPPING THE STUDY PREMATURELY:**

In the unlikely event that there is a security incident (data leak, cyber security incident) that impacts on Isla's visual record platform, the study will be stopped pending investigation of the incident and return to normal operations.

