## 13. ADVERSE EVENTS

Staff witnessing any behaviour on a patient videorecording that is cause for concern should report their concerns immediately to the clinical lead [name], either in person or via email [[contact]](mailto:[contact]). Alternatively, [name] (Matron – Medicine for the Elderly) [[contact]](mailto:[contact]), or [name] (Ward Manager – Medicine for the Elderly) [[contact]](mailto:[contact]), may be contacted.

**A Security Incident** is any incident that occurs by accident or deliberately that impacts Isla's users or the patient data on the system. This could be anything that threatens the confidentiality, integrity or availability of information, data or services delivered by Isla. This includes unauthorised access to, use, disclosure, modification, or destruction of data or services used or provided by Isla. In the unlikely event that there is a security incident, the study will be stopped pending investigation of the incident and return to normal operations.

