## DEFINITIONS

**Adverse Event (AE):** any untoward medical occurrence in a patient or clinical study subject.

**Serious Adverse Event (SAE):** any untoward medical occurrence or effect that:

- **Results in death**
- **Is life-threatening** – *refers to an event in which the subject was at risk of death at the time of the event; it does not refer to an event which hypothetically might have caused death if it were more severe*
- **Requires hospitalisation, or prolongation of existing inpatients' hospitalisation**
- **Results in persistent or significant disability or incapacity**
- **Is a congenital anomaly or birth defect**

Medical judgement should be exercised in deciding whether an AE is serious in other situations. Important AEs that are not immediately life-threatening or do not result in death or hospitalisation but may jeopardise the subject or may require intervention to prevent one of the other outcomes listed in the definition above, should also be considered serious.

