### 5.3.1 Non serious AEs

All such events, whether expected or not, should be recorded.

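### Does the privacy and security row of Table 1 need its own count of Security Incidents?

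*Protocol*

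**What the plan says.** Section 9 lists "No. of videos raising cause for concern reported to the clinical lead" as a secondary outcome. Table 1 repeats it as the only visible measure of the feasibility outcome on privacy and security, to be summarised descriptively.

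Section 13 gives the reporting route: "Staff witnessing any behaviour on a patient videorecording that is cause for concern should report their concerns immediately to the clinical lead". Its next paragraph defines a Security Incident as an event affecting Isla's users or the patient data it holds, and adds: "This includes unauthorised access to, use, disclosure, modification, or destruction of data or services used or provided by Isla".

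The stopping criteria in Section 11 name the same kind of event ("In the unlikely event that there is a security incident (data leak, cyber security incident") and give the consequence: "the study will be stopped pending investigation of the incident and return to normal operations". Section 13 repeats that consequence directly after its definition.

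The adverse event rules are medical in scope. An adverse event is "any untoward medical occurrence in a patient or clinical study subject", and the instruction for non-serious events is "All such events, whether expected or not, should be recorded".

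**The concern.** The protocol itself separates two things: worrying behaviour seen on film, and a breach of the platform or its data. The row labelled privacy and security appears to count only the first. Taken literally, it could read 0 in a study that had suffered a data leak. It could also read above 0 because of a conduct issue with no bearing on privacy.

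That would matter because privacy is central to this intervention. Section 1 reports that earlier studies found video recording acceptable to most people provided that the benefits are clear and the privacy and data protection risks are dealt with. Section 4 says the study is meant to inform the decision on a definitive trial. A privacy and security outcome that omits the event serious enough to halt the study looks like a mismatch between label and measure.

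**Working it through.** The protocol gives no incident rate and no figure to reproduce, so the check is a count of what the text assigns, followed by a reading of what happens when an incident occurs.

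**Measures in Table 1, by outcome row**

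| Outcome row | Visible measures | Analysis entries shown |
|---|---|---|
| Patient/carer acceptability | 3 | 1 |
| Direct care team acceptability | 3 | 4 |
| Patient enrolment | 2 | 1 |
| Barriers and facilitators | 2 | 2 |
| Use of the platform | 2 | 2 |
| Privacy and security | 1 | 2 |
| Perceived impacts | 3 | 3 |
| Total | 16 | 15 |

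Measures: 3 + 3 + 2 + 2 + 2 + 1 + 3 = 16, in 7 rows. The privacy and security row has 1, and it does not count Security Incidents.

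**Is the row complete?** It shows two analysis entries against one measure, while the rows on either side of it pair 2 with 2 and 3 with 3. A second measure may have been lost from the copy read here. The evidence is weak, because other rows are also out of step (3 against 1, 3 against 4, 2 against 1). The Section 9 list does not settle the matter either. At least two other Table 1 measures are missing from that list: the numbers of videos requested, attempted and submitted, and "diversity of study sample (screening/enrolment log". Absence from the list therefore does not prove absence from the table.

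**Is an incident logged elsewhere?**

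- Section 10 has six sources: the screening and enrolment log, the Video Tracker, the questionnaires, the patient and carer interviews, the staff interviews and the view metrics. None is assigned Security Incidents.
- The Video Tracker comes closest, since it records problems met while recording. An accidental mishap during capture or submission could appear there. A later breach of the platform would not.
- The Isla audit log is exported only for view metrics, and the names of viewing staff are removed before storage.
- The two adverse event routes, non-serious and serious, are limited by definition to medical occurrences.

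**What follows if an incident occurs?** Under Section 13, an event that meets the definition stops the study until it has been investigated. Section 11 says the same for a data leak or cyber security incident. If the protocol is followed, the number of recognised incidents that leave no trace in the conduct of the study is 0. Each one produces a halt and an investigation in a single-ward pilot lasting 3 months.

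**Does a result depend on the row?** No power calculation was done, no numerical progression criterion is tied to the row, and the stopping rule acts on the event itself and not on a count. Adding the count would alter none of these.

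**The case for a change.** The strongest case for a change is that being known is not the same as being a defined outcome. Sections 9 and 10 are where this protocol names its outcomes and sources, so a label that promises security should have a measure that delivers it. The Section 13 definition is also broad, reaching anything that threatens the data or the service. Small incidents might be resolved without a formal halt, and the number and type of incidents would tell the designers of a later trial more than the fact that the study was paused. The addition would cost one measure and one line naming a log.

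Part of this stands. The visible text gives Security Incidents no count and no named log, and a count by type would be mildly informative. Three considerations limit it:

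- The measure is not empty of privacy content. Table 1 does not confine it to misconduct, and Section 13 speaks of any behaviour on a recording. That can include a privacy breach caught on film, such as the recording of personal care, which Section 8 rules out.
- Handling a small incident without a halt would depart from Sections 11 and 13 as written. An extra line in Table 1 would not cure that.
- The Trust's Data Protection Impact Assessment and the video-recording SOP are cited but not reproduced in the protocol. Incident logging may be set there; this is unknown either way.

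**Conclusion.** The observation is accurate for the visible text, but it does not call for a change. It is a gap in documentation that the study team would fill without difficulty: a report of this pilot would have to explain any halt, and in doing so would state that a security incident occurred and what kind it was. A 0 in the privacy and security row would not mislead a reader who also learns that the study had been stopped.

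The effect is confined to 1 of 7 outcome rows and 1 of 16 visible measures, all of them descriptive. The row is secondary. The primary outcome, the sample size and the stopping rule are untouched. No probability of a misleading 0 can be given, because the protocol calls an incident unlikely and states no rate.

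This rests on two assumptions: that the halt required by Sections 11 and 13 is applied to every recognised incident, and that the investigation leaves a record the team can report from. An incident that nobody recognised would escape a count in Table 1 just as it would escape the halt.

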## 10. DATA COLLECTION

### ***Screening/Enrolment Log***

The eligibility and enrolment status of all patients screened for the study will be documented on the **Screening/Enrolment Log**; this includes reasons for non-enrolment. This log will be kept in the study file in the Doctor's Office on the Medicine for the Elderly ward. It will be reviewed by and completed by the direct care team and the researcher during the 3-month pilot of Isla's platform.

### ***Video Tracker***

Patient video requests, attempts, submissions, and any issues associated with taking the recordings will be documented on the **Video Tracker**. The Video Tracker will be kept in the study file in the Doctor's Office on the Medicine for the Elderly ward. It will be used during ward rounds to document team decisions about which aspects of a patient participant's condition/functional ability are to be video-recorded. The Video Tracker will also be used to document 'Videos attempted'; 'Videos submitted' and any issues related to video-recording that the team experienced. At the end of the 3-month pilot, the paper records will be scanned and transferred to, and stored in, Imperial College Healthcare NHS Trust's Clinical, Analytics, Research and Evaluation (iCARE) informatics environment.

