#### ***Video View Metrics***

At the end of the 3-month pilot of Isla's platform, video view metrics will be exported from Isla's audit log. Prior to storing the spreadsheet for descriptive analysis, the audit log will be pseudonymised by replacing the patient's name with their study ID and the names of the clinical staff who viewed the videos will be removed. The video view metrics spreadsheet will be transferred to, and stored in, Imperial College Healthcare NHS Trust's Clinical, Analytics, Research and Evaluation (iCARE) informatics environment.

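### The count of videos submitted comes from an unchecked paper tracker, although the submitted videos themselves are held on Isla

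*Protocol*

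**What the plan says.** Section 9, Table 1, lists under direct care team acceptability: "No. of videos requested, attempted & submitted (video tracker". The source of all three counts is therefore fixed in the protocol.

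Section 10, Video Tracker, describes that source. On location: "The Video Tracker will be kept in the study file in the Doctor's Office on the Medicine for the Elderly ward". On content: "The Video Tracker will also be used to document 'Videos attempted'; 'Videos submitted' and any issues related to video-recording that the team experienced". It is a paper form, since at the end of the pilot "the paper records will be scanned and transferred to, and stored in" the Trust's secure data environment. Section 8, How well, states the intended completeness: "Each video-recording request/ attempt/ submission will be documented on the" tracker.

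Section 8 also describes where a submission takes place. Under What: materials and What: procedure, staff must be logged in to Isla to capture a video, and Isla stores it. Under Who, the people recording may be doctors, nurses, healthcare assistants or therapists. Under Where, recording may take place on the ward or "in other areas within St. Mary's hospital where patients' functional abilities are assessed (e.g. hospital staircase, therapy kitchen; therapy gym").

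The only Isla export that the protocol describes is in Section 10, Video View Metrics: at the end of the pilot "video view metrics will be exported from Isla's audit log", with patient names replaced by study IDs.

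**The concern.** The three counts in that row of Table 1 differ in kind. A request is a team decision on a ward round. For an unsuccessful attempt, no Isla record is described. A handwritten log is a reasonable source for both. A submission is different: it leaves a video on the platform whether or not anyone writes it down. For that count the protocol relies on a second, manual entry, made after the recording in a file in the Doctor's Office, and describes no comparison with the platform.

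If some entries are not made, the error runs mainly one way. A video held on Isla but missing from the tracker lowers the submitted count and makes a delivered recording look undelivered, in a measure that is read as staff acceptability. The study is meant to inform a decision on a larger trial, so a recording failure on paper could be mistaken for reluctance or difficulty among staff. The tracker could also disagree with two neighbouring measures, the percentage of patients with a linked video and the view metrics, and the protocol does not say which figure would then stand.

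**Working it through.** **No stated figure to reproduce.** The protocol gives no expected number of videos, no tracker completeness rate and no power calculation. The check is to trace each count to its source and then show how the result depends on an assumed miss rate.

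**Step 1: sources side by side.**

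| Count | Source in Table 1 | Other record described |
|---|---|---|
| Requested | Video Tracker | Daily plan in Cerner and the junior doctors' task list (Section 8, During the pilot) |
| Attempted | Video Tracker | None described |
| Submitted | Video Tracker | The video itself, stored on Isla (Section 8, What: materials and What: procedure) |
| Views | Isla audit log | Not needed |

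Only for *submitted* does the platform hold the thing being counted while the outcome is taken from paper.

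**Step 2: effect on the count.** Let N be the true number of submissions and m the share not entered. The expected tracker count is N × (1 − m). The target of 30 patients is in the protocol. The 1, 2 or 4 videos per patient and the values of m are assumptions.

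| m | N = 30 × 1 = 30 | N = 30 × 2 = 60 | N = 30 × 4 = 120 |
|---|---|---|---|
| 0% | 30 | 60 | 120 |
| 5% | 28.5 | 57 | 114 |
| 10% | 27 | 54 | 108 |
| 20% | 24 | 48 | 96 |
| 30% | 21 | 42 | 84 |

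**Step 3: effect on the ratios.** Let s be the true share of attempts that end in a submission. The result depends on which entries are missed.

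- The attempt is entered but the submission is not: apparent success is s × (1 − m). With s assumed to be 100% and m from 10% to 30%, this is 90% to 70%.
- Attempt and submission are both left out, at the same rate whatever the outcome: apparent success is s × (1 − m) / (1 − m) = s, so this ratio is unchanged.
- In either case, if the request was entered on the ward round, the ratio of submitted to requested is multiplied by (1 − m).

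The requested-to-submitted ratio is therefore exposed under both patterns. The attempted-to-submitted ratio is exposed only under the first.

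**The case against.** The protocol is not without safeguards. Section 8, How well, requires every request, attempt and submission to be logged. Under During the pilot, the team agrees who is accountable for each recording, participants are reviewed daily, the handover list shows whether a patient has a video available, and a sign goes up at the bed once one has been submitted. These cues would prompt someone to complete a missing row. They reduce the risk, but they do not show that the count is complete, and the handover code and bedside sign mark that a patient has a video rather than how many.

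The consequence is also small. The submitted count is not among the primary and secondary outcomes listed at the start of Section 9. It appears only in Table 1, beside questionnaires and interviews, and no test or threshold uses it. Keeping the whole process on one form is coherent, and reconciliation might be left to a data-management or analysis plan that is not at hand. That limits the weight of the point. It does not remove it, because Table 1 itself names the source.

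Several stronger readings are tempting and are not supported:

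- A reader might infer that submissions are already being exported. The text covers view metrics only and does not say that the export lists submissions.
- A reader might infer that Isla's record is stated to be exact. That the platform holds every submitted video follows from how it is used, but the protocol gives no such guarantee.
- A reader might infer that requests exist only on paper. They are also entered in Cerner.
- A reader might infer that under-counting is likely, or concentrated in staff who work away from the office. The protocol gives no miss rate and no information on who completes the form, so both are conjecture.
- A reader might infer that the percentage of patients with a linked video is biased too. Table 1 does not assign that outcome to the tracker and names no source for it.

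**Conclusion.** The point holds as a modest, inexpensive improvement. The submitted count is taken from a handwritten form with no described verification, although the videos being counted are held on Isla. There is a risk of under-counting, partly offset by the logging requirement and the ward prompts. Its size cannot be derived from the protocol: the tables above are illustrations, they assume both the number of videos and the miss rate, and they show no bias when nothing is missed. The 90% to 70% range further assumes that every attempt truly succeeded and that attempts were logged while submissions were not. The effect is confined to one descriptive staff-acceptability measure and the ratios built on it. It does not touch the questionnaires or interviews that inform the same objective.

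**What to change.** - In Section 9, Table 1, and Section 10, Video Tracker, define *submitted* as the number of videos held on Isla for enrolled patients at the end of the pilot.
- In Section 10, Video View Metrics, extend the end-of-pilot export to include a list of submissions, pseudonymised by study ID in the same way as the view metrics. The sponsor should confirm with the platform provider that such a list, with dates, can be produced.
- Keep the tracker as the source for requests, attempts and recording problems.
- Reconcile the tracker with the Isla list by study ID and date, and report how many platform submissions have no tracker entry. That number is itself useful for deciding whether a paper tracker is adequate in a larger trial.

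The cost is one small additional export and the matching of a short list. It needs no new data from patients, carers or staff.
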